If 2 or more doses (consecutive or non-consecutive) of IP are missed, a conversation between the Investigator and the AstraZeneca study physician should take place to review treatment compliance and decide on the participant's further disposition. All participants, regardless of whether they remain on IP or not, will be encouraged to remain in the study through the end of the treatment period (Visit 16). Discontinuation procedures are described in Section 7.1.1).

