7 DISCONTINUATION OF STUDY INTERVENTION AND PARTICIPANT DISCONTINUATION/WITHDRAWAL

7.1 Discontinuation of Study Intervention

Participants who prematurely discontinue from IP will be asked to come in for all visits and study assessments at the IP Discontinuation (IPD)/EOT visit.

Discontinuation from IP does NOT automatically lead to a complete withdrawal from the study. Participants discontinuing from IP are strongly encouraged to continue in the study up to the study completion (Visit 17, Week 60) as described in Section 7.1.1.

Participants will be discontinued from IP in the following situations:

- Participant decision. The participant is at any time free to discontinue treatment, without prejudice to further treatment. The participant should always be asked about the reason(s) and presence of any AEs.
- AE that, in the opinion of the Investigator, contraindicates further dosing
- Severe non-compliance with the CSP
- Risk to participant as judged by the Investigator or AstraZeneca
- Pregnancy
- IP unblinding
- Development of any of the following study-specific criteria for discontinuation:
 - Anaphylactic reaction to IP administration, in the opinion of the Investigator, requiring administration of epinephrine
 - Development of helminth parasitic infestation requiring hospitalisation.

Refer to the SoA ([Table 2](#)) and Section 7.1.1 (IPD visit) for data to be collected at the time of IPD and follow-up and for any further evaluations that need to be completed.

The reason for premature discontinuation of IP should be documented in the source documentation and recorded in the eCRF.

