#### **2.2.1 Important protocol deviations**

Important protocol deviations are a subset of protocol deviations that may significantly impact the completeness, accuracy, and/or reliability of the study data or that may significantly affect a participant's rights, safety, or well-being.

The final list of important protocol deviations will be documented prior to unblinding the study data (primary DBL) and will include but may not be limited to the following categories:

- Eligibility criteria not met (participants incorrectly randomised)
  - Deviations from key inclusion criteria
  - Deviations from key exclusion criteria
- Deviations from informed consent procedures
- Discontinuation criteria for IP met but participant not withdrawn from study treatment
- Deviations from IP management and administration
- Received prohibited/restricted concomitant medication
- Other important protocol deviations
  - Scheduled study assessments not done or incorrectly performed at baseline and/or >3 post-baseline visits in the same year (separately for UPDD assessments, physical examination, vital signs, safety lab tests, pregnancy tests)

- Unblinding of treatment assignment for reasons unrelated to participant safety
- Other severe non-compliance (such deviations will be clearly described in the CSR)

Only important protocol deviations will be summarised and listed in the CSR.

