### **8.1.4 Sensitivity analyses: Primary estimand assuming dropout reason-based multiple imputation approach**

To examine the sensitivity of the results of the primary analysis to departures from the underlying assumptions, additional analyses will be performed. As with the primary analysis the sensitivity analyses include all data until participants withdraw (up to Week 24) from the study regardless of if they discontinue from randomised treatment.

For sensitivity analyses, missing data will be imputed using controlled sequential MI methods based on pattern mixture models ([EMA/CHMP/EWP 2010](#)). This model will assume that some pre-specified subset of participants who withdraw from the study have correlations with future unobserved visits similar to participants in the placebo arm.

The following default assumptions that will be used to impute the missing data are as follows:

- (a) MAR: Assumes that the trajectory for participants who dropped out in each arm is similar to those observed in their own treatment arm. [The primary analysis already implements this approach. It will not be repeated.].
- (b) Dropout Reason-based Multiple Imputation (DRMI): Assumes that the trajectory for participants in the benralizumab arms who dropped out for a treatment related reason or severe non-compliance of protocol is similar to that of the placebo participants,

whereas the remaining participants who has dropped out are imputed assuming MAR.

A summary of reasons for participants withdrawing from the benralizumab treatment arm and the corresponding treatment arm used to calculate the imputation response rate under MAR and DRMI is given in Table 11.

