**Table 11 Parameters for calculating the imputation under MAR and DRMI**

Reason for withdrawal	MAR	DRMI
Adverse Event	Benralizumab	Placebo
Development of study-specific discontinuation criteria*	Benralizumab	Placebo
Death	Benralizumab	Placebo
Severe non-compliance to protocol	Benralizumab	Placebo
Eligibility criteria not fulfilled	Benralizumab	Benralizumab
Participant lost to follow up	Benralizumab	Benralizumab
Participant decision	Benralizumab	Based on review prior to study unblinding
COVID-19	Benralizumab	Benralizumab
Other	Benralizumab	Based on review prior to study unblinding

Note: Participants in the placebo arm are imputed using the mean of the non-missing values in placebo arm.

\* Development of study-specific discontinuation criteria are based on the following: Anaphylactic reaction to the investigational product requiring administration of epinephrine; Development of helminth parasitic infestations requiring hospitalization; If 2 doses of the IP are missed during course of the study; A respiratory-related event requiring mechanical ventilation.

Some reasons for withdrawal are clearer to determine as treatment related (AEs, Death, Development of study-specific discontinuation criteria) or non-treatment related (participants lost to follow up, eligibility criteria not fulfilled). Other reasons are less clear such as participant decision and ‘Other’; a review of each participant who withdraws from the study will therefore be carried out prior to unblinding the study. Based on this review the default assumptions for DRMI as described in b) and Table 11 may be changed. A list of these participants and the assumptions made under DRMI will be documented prior to unblinding of the study.

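### SAP Table 11 names two study-specific discontinuation criteria that protocol Section 7.1 does not list, so some withdrawals could be misclassified in the DRMI sensitivity analysis and in the Kaplan-Meier split by reason

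*SAP*

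**What the plan says.** **Protocol.** Section 7.1 gives general grounds for stopping investigational product (IP) and then two study-specific ones: "Anaphylactic reaction to IP administration, in the opinion of the Investigator, requiring administration of epinephrine" and "Development of helminth parasitic infestation requiring hospitalisation". Missed doses are handled in Section 6.1.2. After 2 or more, "a conversation between the Investigator and the AstraZeneca study physician should take place to review treatment compliance" and to settle what happens next. The same paragraph allows for the participant either staying on IP or coming off it.

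**SAP list.** Table 11 has a row for withdrawal on study-specific criteria. Its footnote begins "Development of study-specific discontinuation criteria are based on the following" and gives four items. The first two match protocol Section 7.1. The other two are "If 2 doses of the IP are missed during course of the study; A respiratory-related event requiring mechanical ventilation".

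**What the SAP does with the list.**
- Section 8.1.4 assumes, for DRMI, that the trajectory of benralizumab participants who "dropped out for a treatment related reason or severe non-compliance of protocol is similar to that of the placebo participants". The text under Table 11 names the study-specific criteria among the reasons that are clearly treatment related. COVID-19 and loss to follow-up keep own-arm imputation.
- Section 8.1.1 commits to Kaplan-Meier plots of time to IP discontinuation and time to study withdrawal, split by whether the reason is treatment related, and takes that definition from Table 11.
- Section 2.2.1 includes among the important deviations "Discontinuation criteria for IP met but participant not withdrawn from study treatment". It does not say which list of criteria is meant.
- Section 6 declares two changes from the protocol: the added extension period analysis set and the wider angioedema analyses. The two extra criteria are not mentioned.

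**The concern.** Table 11 is a classification rule: the reason category decides whether a missing benralizumab outcome is imputed from the participant's own arm or from placebo. If its categories differ from those under which the trial is run, the same withdrawal can be sorted in two ways.

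The missed-dose item is the one that matters. Protocol Section 6.1.2 itself requires IP to be withheld for fever, significant infection or intercurrent illness, and a postponed dose that runs into the next visit window is skipped. SAP Section 2.2.2 expects doses to be missed because of COVID-19. Doses missed by following the protocol can therefore meet a criterion that the SAP calls treatment related. A participant who then withdraws because of COVID-19 fits both the COVID-19 row (own arm) and the study-specific row (placebo), and no row is given precedence.

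At stake are the DRMI estimate, the Kaplan-Meier split by reason and, possibly, the list of important deviations.

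**Working it through.** **Step 1. The lists side by side.**

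| Event | Protocol | SAP Table 11 footnote |
|---|---|---|
| Anaphylactic reaction needing epinephrine | Section 7.1, study-specific criterion | Listed |
| Helminth infestation needing hospital care | Section 7.1, study-specific criterion | Listed |
| 2 missed IP doses | Section 6.1.2, discussion of compliance and disposition | Listed |
| Mechanical ventilation for a respiratory event | Not found in the protocol text available | Listed |

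The protocol has two criteria and the SAP four, so two are unmatched. The protocol appendices were not available, but Section 7.1 is where the protocol sets out this list.

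**Step 2. Which withdrawals would change.** The effect of moving a benralizumab participant into the study-specific row (placebo under DRMI) depends on the row that would otherwise apply.

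| Reason otherwise recorded | DRMI default | Effect of moving |
|---|---|---|
| Adverse event or death | Placebo | None |
| Severe non-compliance | Placebo | None |
| COVID-19, lost to follow-up, eligibility not fulfilled | Benralizumab | Own arm becomes placebo |
| Participant decision, Other | Settled by review before unblinding | Depends on the review |

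A ventilation event would most likely be recorded as an adverse event or death, so that item hardly alters imputation. The missed-dose item alters it mainly in the third line.

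**Step 3. Opportunity before the primary time point.** Three doses precede Week 12 (Weeks 0, 4 and 8; protocol Section 4.1.2), and the full analysis set requires at least one dose. On the planned schedule, a participant reaches Week 12 by this route only by receiving the Week 0 dose, missing Weeks 4 and 8, and leaving the study without a Week 12 itch score (ISS7). Someone who withdraws later keeps the observed Week 12 value. SAP Section 8.1.2 also reports imputed results at Week 24. Six doses precede that visit (Weeks 0 to 20), so there is more room for the problem there.

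**Step 4. Size.** The plan gives no figure on this point. The only relevant planning inputs are in protocol Section 9.2: difference 4.7, SD 6, 60 per dose and 40 on placebo, 10% dropout, two-sided 2.5% level, stated power 90%.

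Check of those inputs: 10% dropout leaves 54 and 36. The standard error is 6 × √(1/54 + 1/36) = 1.29, and 4.7/1.29 = 3.64. Power is 91.9% by the normal approximation and 91.1% by the noncentral t, so the stated 90% is reproduced. The mismatch between the lists does not enter this calculation.

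Illustrative shift: if k of the 60 participants in a dose arm move from own-arm to placebo imputation, and the full 4.7 points separates the two, the arm mean moves by 4.7 × k/60.
- k = 1: 4.7/60 = 0.078 points, about 6% of the standard error (0.078/1.29 = 0.06).
- k = 6, which is the arm's whole planned 10% dropout: 0.47 points, so 4.7 becomes 4.23. This is a ceiling, not a forecast.

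**The case against.** The strongest reply is that little depends on the footnote, and much of that reply stands.

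- **Reach.** The primary mixed model, the key secondary test and the multiplicity procedure do not use Table 11. SAP Section 4.2.6.3 makes the missing-data sensitivity analyses optional, subject to the amount of missing data, although Section 8.1.4 is worded as a commitment. This stands for DRMI. It does not cover the Kaplan-Meier split in Section 8.1.1, which carries no such condition and includes IP discontinuation as well as study withdrawal.
- **Safeguard.** Each withdrawal is reviewed before unblinding, the Table 11 defaults may be changed, and the assumptions are documented. This reduces the risk. It does not remove it, because the review is motivated by the unclear reasons, whereas the study-specific category is named as a clear one.
- **Table 11 is keyed to the reason for withdrawal.** Having missed 2 doses at some time does not by itself move a participant who leaves for another reason. That is fair, and it is why the consequence is only possible. The SAP gives no rule for a withdrawal that fits two rows.

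Three stronger readings are tempting. The first is that the SAP makes every participant who misses 2 doses and continues an important deviator. Section 2.2.1 does not cite the Table 11 footnote and can equally be read as meaning the protocol's own criteria, so this depends on the reading. The second is that recorded withdrawal reasons will follow the protocol and clash with the SAP. No case report form is among the documents, and if its reasons did follow the protocol, the footnote would reclassify nobody unless someone re-derived the reason. The third is that several participants per arm would move at Week 12. Step 3 shows how narrow that route is, and no document supports a count.

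**Conclusion.** The inconsistency is real, and the text reviewed does not resolve it. The SAP applies a four-item list where the protocol has two, treats one of the extra items differently from protocol Section 6.1.2, and does not declare the difference. As written, a withdrawal after 2 missed doses could be misclassified in DRMI and in the Kaplan-Meier split by reason. Whether the list of important deviations is also affected depends on which criteria Section 2.2.1 is taken to mean.

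The effect is small. For DRMI it is at most about 0.08 points per reclassified participant in an arm of 60. That assumes the planned 4.7-point effect holds and separates the two imputations in full. Section 8.1.2 imputes by regression, so earlier observed scores could make the shift smaller. A reader might infer that the primary result or the power is in doubt; the documents do not support that, since neither uses Table 11. Whether an earlier protocol version carried the extra items cannot be checked from the text available.

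**What to change.** Before unblinding:

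1. Reconcile protocol Sections 6.1.2 and 7.1 with the SAP Table 11 footnote. No position is taken here on which clinical rule is right.
2. Have Table 11 and SAP Section 2.2.1 cite the reconciled protocol section instead of keeping a separate list.
3. State which Table 11 row takes precedence when a withdrawal fits more than one, and apply the same rule to the Kaplan-Meier split in Section 8.1.1.
4. If any difference from the protocol is intended, record it in SAP Section 6.

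If only the SAP changes, the cost is a footnote, a cross-reference and one added sentence. If the reconciliation changes the protocol, it also needs a protocol amendment. No analysis model or sample size changes in either case.

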### **8.1.5 Overall summary of analyses to account for missing data**

Forest plots will be used to show the primary analysis results along with the missing data sensitivity and alternative estimand analysis results.

It is noted that if the primary analysis is statistically significant, it is not necessarily expected that all sensitivity analyses will also give statistically significant results. If the results of the sensitivity analyses provide reasonably similar estimates of the treatment effect to the primary analysis, this will be interpreted as providing assurance that neither the lost information nor

the mechanisms which cause the data to be missing have an important effect on primary analysis conclusions. Based on these outputs and the drug's mechanism of action, the plausibility of the assumptions we make about missing data in the different analyses will be considered and described in the clinical study report.

The methodology described above to explore any potential impact of missing data for the ISS7 change at Week 12 endpoint may be repeated for other endpoints if required due to amount or pattern of missing data.

## 8.2 Analysis plan for immunogenicity data

Serum samples for ADA assessments will be conducted utilizing a tiered approach (screen, confirm, titre) and ADA data will be collected at scheduled visits shown in the CSP. ADA result from each sample will be reported as either positive or negative. If the sample is positive, the ADA titre will be reported as well.

In general, participants with a missing baseline ADA assessment will be assumed to be ADA negative at baseline as a conservative approach to ensure that all participants are included in all analyses. If a positive ADA titre result is reported as  $\leq 50$ , then the titre will be imputed as 50 for titre summaries. ADA results from samples collected post-dose instead of pre-dose on an IP administration day are considered unreliable and should be excluded from all derivations.

For each participant, the following ADA responses will be evaluated over the entire on-study period through EOT:

- Participants who are ADA positive at any time during the study, including baseline and/or post-baseline (also generally referred to as ADA positive). The proportion of ADA positive participants in a population is known as ADA prevalence.
- Participants who are ADA negative at all assessments, including baseline and postbaseline (also generally referred to as ADA negative).
- Participants who are ADA positive at baseline only.
- Participants who are ADA positive at baseline and at least one post-baseline assessment.
- Treatment-emergent ADA positive (referred to as ADA incidence). A positive postbaseline result and either of the following statements holds:
  - Baseline is ADA negative and at least one post-baseline assessment is ADA positive. This is called treatment-induced ADA positive.
  - Baseline is ADA positive, and the baseline titre is boosted by greater than the variability of the assay (i.e.  $\geq 4$ -fold increase) at  $\geq 1$  post-baseline timepoint. This is called treatment-boosted ADA positive.
- Participants who are persistently ADA positive, which is defined as ADA negative at baseline and having at least 2 post-baseline ADA positive measurements with  $\geq 16$  weeks between first and last positive, or an ADA positive result at the last available post baseline assessment.
- Participants who are transiently ADA positive, defined as ADA negative at baseline and at least one post- baseline ADA positive measurement and not fulfilling the conditions for persistently positive.
- Participants who are ADA positive with maximum titre  $>$  median of maximum titres. The median of maximum titres will be calculated based on the maximum titre of each ADA positive participant within each treatment group (including both baseline and post-baseline measurements).

The responses above will be summarised as counts and percentages by treatment group. The maximum ADA titre over the on-study period will also be summarised for participants in each of the ADA positive response categories listed above. The maximum titre will be derived based on all available ADA titres reported for each participant, including any unscheduled assessments.

ADA response (positive or negative) and titre will be summarised at baseline and at all scheduled post-baseline visits by treatment group. In the event a participant has more than one result within a given visit window, the maximum ADA titre will be used in the by-visit summary. In addition, the ADA response will be presented cumulatively. The cumulative ADA response is positive for a specific visit if a positive ADA result is detected at any time point up to and including the specific visit. If all ADA result are negative up to the specific visit, then the cumulative ADA response is negative for that visit. A summary of the number and percentage of participants who are ADA positive at a post-baseline assessment for the first time by visit will also be presented. A line plot of the proportion of participants who are ADA positive at each visit will be provided.

The proportion of participants with ADA persistently positive response will be summarised by visit and treatment group.

Key participant information will be listed for participants with positive ADA results, including ADA status, titer, benralizumab serum concentration, and eosinophil level.

All analyses will be conducted on the safety analysis set by treatment group unless otherwise specified. All ADA results will be listed.

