Post-menopause confirmation (FSH)	X	-	-	-	-	-	-	-	-	-	-	-	-	-	-	-	-	-	Section 8.2.1.1
Hepatitis/HIV screening	X	-	-	-	-	-	-	-	-	-	-	-	-	-	-	-	-	-	Section 8.2.1.2
Pharmacokinetics sample prior to IP administration	-	X	X	-	X	-	X	-	-	X	-	-	X	-	-	-	-	-	Section 8.5.1
Immunogenicity sample (ADA)	-	X	-	-	X	-	X	-	-	X	-	-	X	-	-	-	-	-	Section 8.5.2
CCI																			

Table 2 Schedule of Site Visit Activities

Procedure	Run-in	Double-blind placebo-controlled treatment period						Double-blind extension period						Follow-up		
Visit	1	2	3	4	5	6	7	8	9	10	11	12	13	14	15	16
Week ^a	-4 wk to -10 days ^b	0	4	8	12	16	20	24	28	32	36	40	44	48	52	60
IP administration ^f	-	X	X	X	X	X	X	X	X	X	X	X	X	X	-	-
CC1																
Skin biopsy	-	X	-	-	X	-	-	X	-	-	-	-	-	-	-	Section 8.6
Investigational product administration																
IP administration ^f	-	X	X	X	X	X	X	X	X	X	X	X	X	X	-	-

^a The window for Visits 3 through 16 will be \pm 3 days.

^b The run-in period is a maximum of 4 weeks and minimum of 10 days.

^c Unscheduled Visit: may be initiated as needed; procedures should be performed as clinically indicated at the discretion of the Investigator.

^d Investigational Product Discontinuation: In case of early discontinuation from investigational product, visit procedures should be performed 4 weeks \pm 7 days after the last dose of IP or as soon as feasible if this interval is missed (eg, if decision on discontinuation was made later). Note: The IPD visit replaces the nearest regular visit.

^e It is recommended that vital signs are assessed before any interventional study procedures (blood test collection, IP administration).

^f Review of self-administration of IP procedures may be offered at Visits 2 and 3.

ADA, Anti-drug antibodies; AE, Adverse Event; ECG, Electrocardiogram; EOT, End of treatment; FSH, Follicle-stimulating hormone; HIV, human immunodeficiency virus; IP, Investigational product; IPD, Investigational Product Discontinuation; PRO, Patient-reported outcomes.

All within-window PRO assessments (Table 3) that have not been completed prior to a site visit will be completed at the site before any other study procedures are conducted.

Table 3 Schedule of PRO Assessments

Instruments	Schedule
Daily PRO: UPDD Question 1	Every morning ^a . First assessment at home the day after Visit 1.
Daily PROs: UPDD Questions 2-7	Every evening ^b . First assessment at home on the day of Visit 1.

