### **2.1.3 Safety analysis set**

The safety analysis set will comprise all participants who receive at least one dose of IP. Participants will be classified according to the treatment they actually received.

Erroneously-treated participants (eg, those randomised to treatment A but actually given treatment B) will be included in the group of the treatment they received. A participant who receives at least one dose of active IP will be classified as active and included in the active IP treatment group. A participant who receives both active dose regimens will be classified as the higher active dose regimen (ie, 60 mg). Any deviations from the randomised treatment will be listed and considered when interpreting the safety data.

All safety summaries and anti-drug antibodies (ADA) analyses will be based on this analysis set.

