## 4.1 General principles

The primary efficacy analyses will be based on the double-blind, 12-week placebo-controlled induction period, including data up to Week 24. Efficacy endpoints will be analysed using the FAS, the analysis of safety endpoints will be based on the safety analysis set. Analysis sets are defined in Section [2](#).

Summary data will be presented in tabular format by treatment group. Categorical data will be summarised using frequency and percentages, where the denominator for calculation is the underlying analysis set population unless otherwise stated. Continuous data will be summarised with descriptive statistics of number of available observations, mean, standard deviation (SD), median, minimum and maximum, and quartiles where more appropriate. Data listings will be sorted by treatment and participant number.

All point estimates will be presented together with 95% confidence intervals (CIs) as measures of precision and nominal 2-sided p-values, rounded to 4 decimal places.

The primary estimand, analysed using the treatment-policy strategy, is the difference in mean change from baseline at Week 12 in ISS7 between each benralizumab dose and placebo, using the full analysis set, including all data up to week 12 regardless of discontinuation of IP or whether use of rescue medication has or has not occurred. As all participants who prematurely discontinue from IP in the study are asked to come in for all visits and study assessments up to Week 52, the amount of missing data expected in the analysis is assumed to be low and this estimand strategy is considered appropriate. However, sensitivity analyses may be performed to assess the robustness of the efficacy results to the missing data assumptions as described in [Appendix 8.1](#).

As described above, in general analyses will follow an ITT principle; while changes to background medications for CSU and related treatments are discouraged, if any do occur, data following any changes to background therapies, or post missed doses or discontinuation of IP will still be included in the analyses. However, sensitivity analyses may be performed to assess any impact of changes in study and background medications if deemed appropriate (see Section [4.2.6.3](#) and [Appendix 8.1](#)).

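### The SAP sets no evaluable denominator for ADA percentages, so its default rule dilutes ADA incidence and by-visit positivity by the share of participants without a result

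*SAP*

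**What the plan says.** Three rules together fix the denominator.

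- SAP 4.1, on categorical summaries: "where the denominator for calculation is the underlying analysis set population unless otherwise stated".
- SAP 8.2, on ADA: "All analyses will be conducted on the safety analysis set by treatment group unless otherwise specified". SAP 2.1.3 likewise assigns ADA analyses to the safety set.
- SAP 2.1.3, on membership: "The safety analysis set will comprise all participants who receive at least one dose of IP". No ADA result is needed.

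Section 8.2 gives no different denominator, either for the study-level categories (prevalence, treatment-emergent, persistent, transient) or for the by-visit table and line plot.

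The only rule in 8.2 for an absent ADA result concerns baseline: "participants with a missing baseline ADA assessment will be assumed to be ADA negative at baseline as a conservative approach". Its stated purpose is "to ensure that all participants are included in all analyses". Section 8.2 also discards samples taken after dosing on an administration day, which creates further missing results.

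The negative class is defined as "Participants who are ADA negative at all assessments, including baseline and postbaseline", with no minimum number of post-baseline results. The cumulative by-visit response is negative when every result up to that visit is negative.

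**The concern.** Treatment-emergent ADA requires a positive post-baseline result. A dosed participant with no such result can never enter the numerator but stays in the denominator. The same holds at each visit for anyone not sampled there. A plotted proportion positive could therefore fall through attrition alone, with no change in immunogenicity.

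ADA is listed among the secondary endpoints, and protocol 2.3 names reduced efficacy and hypersensitivity as potential risks of developing it. The dilution makes the product look slightly less immunogenic. It would also differ between dose groups if the untested share differed.

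The SAP sets evaluable-only rules elsewhere. The laboratory and urinalysis shift tables in 4.2.8.2 need both baseline and post-baseline data, and the PK set in 2.1.4 needs a quantifiable post-dose observation. Section 3.3.2 gives an explicit rule for missing UAS7 response. ADA has no counterpart, so a programmer would fall back on the 4.1 default.

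**Working it through.** The documents give no expected ADA rate, so there is no planned figure to reproduce. The check is on the arithmetic of the denominator.

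**Inputs**
- N = 60 per induction dose (SAP 1.2) and 30 per randomised sequence (SAP 1.1.1).
- m = share with no evaluable result. The only dropout figure is 10%, assumed for the Week 12 ISS7 power calculation (SAP 1.2). Values of 20% and 30% are assumptions for late visits.
- p = percentage positive among those tested, assumed 5% to 20%.
- Only benralizumab recipients matter here, because SAP 8.2.1 says the placebo group is not tested.

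**Formula**
- Positives: x = p × N(1 − m).
- Percentage under the SAP default: x/N = p(1 − m).
- Percentage among those tested: x/[N(1 − m)] = p.
- Ratio: 1 − m, whatever p is. The relative understatement is exactly m.

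**Study-level incidence, N = 60, m = 10%**
- Evaluable: 60 × 0.90 = 54. With 6 positives: 6/60 = 10.0% against 6/54 = 11.1%.
- Across p = 5% to 20%, the loss is p × m = 0.5 to 2.0 percentage points.
- The whole-set figure is also the lowest value that the data allow. If all 6 untested participants had been positive, the result would be 12/60 = 20.0%.
- This example treats the whole 10% as lost before any post-baseline ADA sample, so it sits at the upper end.

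**By-visit positivity under the default**

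| Positive among tested | m = 10% | m = 20% | m = 30% |
|---|---|---|---|
| 5% | 4.5% | 4.0% | 3.5% |
| 10% | 9.0% | 8.0% | 7.0% |
| 20% | 18.0% | 16.0% | 14.0% |

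Reading along a row shows the artefact: true positivity is constant, yet the plotted line falls. For one sequence of 30 with 4 positives, 4/30 = 13.3% is reported, against 4/24 = 16.7% with 20% absent or 4/21 = 19.0% with 30% absent.

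**Which figure grows with attrition.** By-visit m rises as participants leave. Study-level incidence loses only those with no post-baseline result at all; someone who gives one sample and leaves later is evaluable and adds nothing to this error.

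**Classification.** Take a participant with a negative baseline sample and nothing afterwards. The study-level definition of negative can be read either way: all existing results are negative, but the definition also refers to post-baseline assessments. The cumulative rule, read literally, carries this participant as negative at every later visit.

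**The case against.** The strongest reply is that much of this is a default reading, that the effect is small, and that nothing inferential depends on it. Several parts stand.

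- A reader might infer that the SAP counts untested participants as ADA negative. It does not say so. The one imputation rule covers a missing baseline, and it can push incidence up, because a later positive then becomes treatment-induced. Only the cumulative rule, taken literally, carries an unsampled participant forward as negative.
- A reader might infer that incidence is understated more and more as participants leave. That holds for by-visit percentages only.
- A reader might infer that the ADA-negative group is contaminated throughout 8.2.1 to 8.2.4. The documents do not support that. Section 8.2.4 uses the PK set, and 8.2.3 and 8.2.4 summarise by visit, where someone who has left contributes no later data. What remains is mainly 8.2.1 and 8.2.2, which are descriptive and conditional on enough data.
- Participants who stop treatment are asked to keep attending (SAP 4.1; protocol 7.1.1.1), so m should be low. Study withdrawal, telephone-only follow-up and unusable samples remain.
- The exact 95% interval for 6/60 runs from 3.8% to 20.5%, far wider than the gap of 1.1 points. That is true, but the dilution has a known direction and can be removed.
- Counts are reported and all ADA results are listed, so the tested number can be reconstructed. The printed percentages and the plot would still be diluted.
- SAP 3.1.3 leaves empty visit windows as missing. That keeps an absent participant out of the numerator; it does not take them out of the denominator.

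**Conclusion.** The concern holds in a limited form. Sections 4.1, 2.1.3 and 8.2, applied as written, give ADA percentages over all dosed participants and understate the percentage among those tested by exactly the untested share. For study-level incidence this is modest: about 1 point in the 6/60 example, and 0.5 to 2.0 points at 10% untested for assumed rates of 5% to 20%. By-visit figures can be affected more, by up to 6.0 points at an assumed 20% rate with 30% absent, and the line plot can show a spurious decline. The class of a participant with only a negative baseline sample is undefined rather than wrongly defined.

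The sizes rest on assumed ADA rates, on assumed absences above 10%, and on placing all of the 10% before the first post-baseline sample. The columns of the ADA row in protocol Table 2 cannot be read with certainty in the available text, so no sampling visit is relied on. The primary, key secondary and multiplicity results are unaffected.

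**What to change.** In SAP 8.2:

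1. Calculate treatment-emergent, persistent and transient percentages among participants with at least one evaluable post-baseline ADA result, and prevalence among those with at least one ADA result of any kind.
2. Calculate by-visit percentages, and the line plot, among those with a result at that visit. Show the numbers tested and missing for each group and visit.
3. Class a participant as ADA negative only if at least one post-baseline result exists, and apply the same condition to the cumulative response. Report baseline-only participants separately as not evaluable.

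The cost is SAP wording and a denominator flag in the programs. No new data are needed, and reported ADA rates become slightly higher. The change does not correct for shorter observation in participants who give an early negative sample and then leave; the numbers tested at each visit would at least make that visible.
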